1.2 Emotional Function Testing

Toronto Alexithymia Scale (TAS): Alexithymia refers to the condition of having trouble identifying and describing emotions, and minimizing emotional experience while focusing attention externally. The TAS is a well-validated and commonly used 20-item instrument to measure alexithymia. It is a self-reported scale with 3 subscales: describing emotions, identifying emotions, and externally-oriented thinking; each item is rated using a 5-point Likert scale whereby 1 = strongly disagree and 5 = strongly agree. The total alexithymia score is the sum of responses to all 20 items, while the score for each subscale factor is the sum of the responses to that subscale: equal to or less than 51 indicates non-alexithymia, equal to or greater than 61 indicates alexithymia. Scores of 52 to 60 indicate possible alexithymia. The scale demonstrates good internal consistency (Cronbach's alpha = .81) and test-retest reliability (.77, p<.01). Research using the TAS-20 demonstrates adequate levels of convergent and concurrent validity. The 3 factor structure was found to be theoretically congruent with the alexithymia construct. In addition, it has been found to be stable and replicable across clinical and nonclinical populations (Bagby, Parker et al. 1994; Bagby, Taylor et al. 1994).

Emotional Function Battery

For a comprehensive objective measurement of emotional function, we will employ paradigms from basic affective science to comprehensively assess multiple aspects of emotional function, including emotional recognition, reactivity, and regulation in an ecologically valid manner using film clips (Werner, Roberts et al. 2007; Goodkind, Gyurak et al. 2010).

a. Emotional Reactivity: Patients will view a series of short (~3 min.) film clips that have been selected for their ability to produce particular positive and negative emotions (Gross and Levenson 1993; Gross 2007). During each film, physiological responses will be measured and facial behavior will be coded. Following each film clip patients will be asked to provide subjective ratings of the nature and intensity of their emotional responses to the film clips. **Film clips intended to induce happiness, sadness, fear, and neutral emotion will be used.**

b. Emotion Recognition: Following each of the reactivity film clips described above, participants will also be asked to identify how the characters in the clips were feeling. Answers will be scored based on predetermined correct responses. We will also use picture stimuli to sample a broader range of positive and negative emotions for patients to identify.

c. Emotional Regulation. Both instructed and uninstructed (or spontaneous) emotion regulation will be assessed. Physiological, behavioral and subject responses will be measured under several conditions. Patients will watch films that are known to produce the emotion of disgust under three different instructional conditions: suppress, amplify, no regulation (Gyurak, Goodkind et al. 2012). The emotion of disgust will be used because it is highly arousing and one of the easiest emotions to elicit in the laboratory context. The instructions for each condition are based on previous research, are as follows: *"We will now be showing you a short film clip. It is important to us that you watch the film clip carefully. (Suppress: "Watch the film clip carefully. If you have any feelings as you watch the film clip, please try your best not to let those feelings show."*

Amplify: “Watch the film clip carefully. If you have any feelings as you watch the film clip, try your best to let those feelings show.” **No regulation:** “Watch the clip carefully”).

Startle responses

Startle probes have been used previously as reliable indicators of emotional reactivity and regulation. At the end of the experimental session, we will administer the following startle probes:

a. Unwarned Startle. Emotional reactivity will also be assessed in response to an unwarmed, high intensity (115 dB, 100ms) acoustic startle that sounds like a gunshot going off behind the head. The response to this probe consists of two reactions, starting with the primary defensive response, which includes a sequence of motor responses to protect the body (eye closure, shoulder raise) as well as increased electrodermal activity (Ekman, Levenson et al. 1983). The secondary response involves an emotional reaction to the primary startle. The high intensity acoustic startle taps into very basic, low-level aspects of defensive reactivity that are largely brain-stem mediated, as well as more complex aspects of emotion response as individuals reflect on their primary reaction (a typical secondary response includes behavioral displays and self-reports of embarrassment/amusement) (Sturm, Rosen et al. 2006). The simple startle probe also offers the advantage of being a reliable elicitor of response across individuals and being a highly controlled and easily standardized stimulus. Physiological, behavioral, and subjective responses to the unwarmed startle will be assessed.

b. Uninstructed Emotion Regulation (anticipated startle). The startle task described above will be repeated, but this time participants will be warned that they will be startled again. A 20-second countdown will signify exactly when the startle will occur. Previous research has shown that people typically “brace” themselves during the countdown and spontaneously recruit regulatory strategies to control their reactions.

1.3 Quality of Life Measurements

Quality of Life will be measured with the Quality of Life Enjoyment and Satisfaction Questionnaire – Short Form (Q-LES-Q – SF), a 16-item scale that measures general well-being and, is among the most frequently used outcome measures in psychiatry research (Endicott, Nee et al. 1993). The internal consistency and test-retest coefficients were 0.9 and 0.93, respectfully. Almost all items significantly correlate to the total score and other measures used in the study, with the correlations ranging 0.41–0.81. The responsiveness parameters indicate Q-LES-Q – SF is 80% sensitive and 100% specific. The psychometric properties of the questionnaire indicate that it can produce reliable and valid clinical assessments of quality of life (Stevanovic 2011).

1.4 Resting functional connectivity MRI

T1- and T2-weighted anatomic images will first be obtained to identify focal lesions. 3D magnetization prepared rapid acquisition gradient echo (MPRAGE) will be used to produce reference images of overlying resting state fMRI activation maps. To capture resting state images, subjects will be instructed to keep their eyes closed and to remain motionless in the scanner. Whole-brain images will be collected using a T2-weighted gradientech echoplanar

imaging sequence (repetition time_3000 ms, echo time_35 ms, number of slices_35, slice thickness_4 mm, matrix size_128_128, and field of view_220_220 mm) on a 3T scanner.

1.5 Intervention with active and sham tDCS and computerized cognitive re-training

After providing informed consent approved by the IRB of New York University School of Medicine (NYUSoM), all patients will undergo testing with the above listed outcome measures. They will then be randomized into the two intervention groups, the groups being (1) tDCS + cognitive re-training, and (2) sham tDCS + cognitive re-training. The intervention will be carried out for 20 minutes twice a week for 6 weeks during which the subjects in each group will be engaged in re-training using visual cognitive re-training software programs for 30-45 minutes during each session (www.positscience.com). These re-training programs have been used in patients with TBI and have been shown to be effective (Fisk, Novack et al. 2002; Calvanio, Williams et al. 2004; Novack, Banos et al. 2006). Cognitive re-training will thus be individualized to each patient's cognitive level, but still be systematic, and will not need direct one-on-one supervision by a neuropsychologist.

Transcranial direct current stimulation will be delivered by trained study personnel using the saline-soaked pair of surface sponge electrodes (35 cm²) delivered by a specially developed, battery-driven, constant direct current stimulator (Fisher Wallace Cranial Stimulator, Fisher Wallace Laboratories, New York) with a maximum output of 4 mA (**Fig. 1**). FDA approval: The Cranial Stimulator is an FDA cleared device indicated for application of electrical stimulation to a patient's head to treat insomnia, depression, or anxiety. TBI subjects experience insomnia, depression and anxiety and all subjects enrolled in this study will have some combination of these problems. The purpose of this study is to understand the mechanisms behind the depression, anxiety and insomnia that patients with TBI experience. The hypothesis is that emotional dysregulation contributes to the symptoms. This device will therefore be used in alignment with FDA clearance indications. To stimulate the DLPFC, the anode electrode will be placed over F3 according to the 10-20 international system for EEG electrode placement (Fregni, Boggio et al. 2005) (**Fig.2**). The cathode will be placed over the contralateral supraorbital area.

Fig.1. FDA approved Fisher Wallace Cranial Stimulator.

[figure not shown]

Fig.2. Placement of electrodes (Rosa and Lisanby 2012).

We will focus our investigations on the left DLPFC, as modulation of this area by tDCS has been shown to enhance working memory (Fregni, Boggio et al. 2005) which also demands similar attentional resources as emotional control (Anderson and Knight 2010). A constant current of 2 mA intensity will be applied for 20 min. Patients will feel the current as an itching sensation at both electrodes at the beginning of the stimulation. For sham stimulation, the electrodes will be placed in the same position; however, the stimulator will be turned off after 5 seconds (Siebner, Lang et al. 2004) so that patients will feel the initial itching sensation in the beginning, but receive no current for the rest of the stimulation period; this procedure has

been used to blind patients to the stimulation condition (Nitsche, Liebetanz et al. 2003; Nitsche, Schauenburg et al. 2003).

2. Data Analysis and Data Monitoring.

Power Analysis: This is a pilot feasibility study hence sample size is small and arbitrary. Power analysis from these pilot data will be used to determine sample size in future studies. Subjects with TBI will be randomized to the 2 treatment groups n=10 in each group.

Data Analysis:

1) To examine the relationship between alerting, orienting and executive attention and emotional recognition, reactivity and regulation in patients with TBI and controls.

Hypothesis: Patients with TBI will show clear patterns of attentional and emotional impairment compared with controls. Deficits in executive attention will be related to deficits in emotional appraisal in patients.

Scoring of emotional recognition, reactivity and regulation:

- 1) **Emotional reactivity film clips:** Physiological responses (cardiac inter-beat, finger pulse amplitude, finger pulse transmission time, ear pulse transmission time, and respiration period) will be recorded, and input from baseline will be subtracted from input across the most intense segment of the clip. Data will be combined into a single aggregate score for each diagnostic group to increase reliability and reduce noise; aggregate scores of patients and controls will then be compared. Facial behavior will be recorded and coded for displays of the target emotion across the most intense segment of the clip; data from patients and controls will then be compared.
- 2) **Emotional recognition:** Responses to emotion recognition questions, using both the reactivity film clips described above and picture stimuli will be recorded and coded; coded data from patients and controls will be compared.
- 3) **Emotional regulation with disgust videos:** For the three conditions, physiological responses (as described above) will be recorded, and input from baseline will be subtracted from input across the most intense segment of the clip. Facial behavior will be recorded and coded. Data from patients and controls will be compared.

For coding facial behavior, coders will be blind to the diagnostic status of the participant and code videos with sound muted; coding will be assessed for inter-rater reliability

Pearson's correlation analysis will be performed to examine the relationship between reaction time (RT) scores indicating alerting, orienting and executive attention on the ANT-R and emotional recognition, reactivity and regulation scores. Differences in patients and controls will be computed. We will also correlate the clinical scores on the MARS with the ANT-R and the TAS-20 scores with the emotional battery scores. We expect that deficits in selective or executive attention will be related to deficits in emotional appraisal in the patients.

2) To determine whether anodal tDCS applied over the dorsolateral prefrontal cortex in conjunction with computer assisted cognitive re-training of attention will lead to greater improvement in attention and/or emotional regulation compared with sham-tDCS + cognitive re-training. Hypothesis: Patients receiving tDCS + cognitive re-training will show greater improvement in post-intervention measures of attention and emotional regulation.

A 2 (condition) x 2 (pre and post session) repeated measures ANOVA with a priori orthogonal contrasts will be performed on the variables related to executive attention and emotional appraisal to determine whether there is a difference both within and between groups. This analysis will also provide data for power analysis to determine the sample size for subsequent interventional studies. We expect that patients receiving tDCS + cognitive re-training will show greater improvement in post-intervention measures of attention and emotional regulation.

3) To determine whether the tDCS intervention produces stronger functional connectivity between fronto-limbic networks compared with sham-tDCS. Hypothesis: Patients receiving tDCS + cognitive re-training will show higher temporal correlation between the frontal and limbic areas compared to baseline than patients receiving sham tDCS + cognitive re-training.

Analyses of the resting state fMRI images will be performed using AFNI and FSL software packages (www.fmrib.ox.ac.uk/fsl/) using standard procedures. The images will be slice-time corrected, despiked, and motion corrected using AFNI, and time series detrending will be performed. The Brain Extraction Tool (Smith 2002; Smith, Jenkinson et al. 2004; Woolrich, Jbabdi et al. 2009) (BET) will be used to skull strip the images, which will be spatially smoothed using a Gaussian kernel. In the first stage analysis, data from each subject will be individually modeled. The stimulus time course will be convolved with a gamma function and the general linear model (GLM) will be employed with motion parameters as covariates. Additionally we will use temporal bandpass filtering (0.01 Hz < f < 0.1Hz), regression of the six motion parameters and of white matter and cerebrospinal fluid signals. Average resting state time series will be obtained for all the seeds of interest, particularly in the **cingulate motor cortex, and dorsolateral premotor cortex** based on prior studies.(Marshall, Zarahn et al. 2009) FSL FEAT will be employed to find the brain voxels that correlate with the seed time series in each subject. Individual functional connectivity maps will be registered to the MNI space and entered into group-level analyses. Higher level analyses will be carried out using FEAT. Connectivity patterns pre- and post-treatment will be compared for all the seeds of interest. Gaussian random field theory will be used for cluster-level multiple comparisons correction (minimum $Z > 2.3$; $p < .05$, corrected) for the resting state analyses.

Data Monitoring: The PI will be overall responsible for data monitoring.

(1) Types of Data or Events: All accumulated outcome data, enrollment numbers, reportable event data (including adverse reactions and unanticipated problems) and overall compliance with the protocol will be monitored.

(2) Responsibilities and roles for gathering, evaluating, and monitoring the data: The PI will be responsible for monitoring the data collected, including data related to adverse events and

unanticipated problems. Accuracy of data collection from assessments at the Motor Recovery Laboratory will be verified on an ongoing basis and at weekly lab meetings. Compliance with the protocol will be verified by the PI and co-investigators. Independence of judgment will be assured by using independent assessors for outcomes.

(3) Reporting adverse events and unanticipated problems to the monitoring entity: Any adverse reaction to the assessment procedures or intervention procedures, although expected to be minimal, will be reported to and compiled by the PI and Co-PI jointly on an ongoing basis. Reportable events will be reported by the PI to the IRB at NYU Medical Center within 5 business days.

(4) Assessments: Assessments will be performed on a quarterly basis to review and assess all the data or events captured under the Data Monitoring Plan to examine any "unanticipated problems involving risks to participants or others" (i.e., as to whether they are unexpected, related to the research, or harmful).

(5) Criteria for action: If significant research-related and harmful adverse events are found at the quarterly assessments, the study will be terminated.

(6) Procedures for communicating; dissemination of safety information: Outcomes of monitoring entity reviews will be communicated to the IRB at NYU Medical Center annually unless there are reportable adverse events or criteria for action.

3. Data Storage and Confidentiality. Data from assessments at the Motor Recovery Laboratory will be stored securely in the PI's office,, at the Rusk Institute of Rehabilitation Medicine, NYU Medical Center. All data will be labeled by subject codes only, and stored on password-protected computers and/or in locked filing cabinets in the secure offices of the PI. Videotapes of the assessments will be stored on password-protected computers and servers, and backed up on DVDs stored in locked cabinets, in the secure offices of the PI. Videotapes will be stored for at least 3 years following the conclusion of the study, and may be stored indefinitely thereafter. Data collection computers will be in locked, fixed locations (no mobile laptops), password protected, and on local networks. Only the PI and her HIPAA certified delegates will have access to the data.

4. Data Stored for Future use: Data will be labeled with unique codes. Only the PI and the study coordinator will have access to the code. This information will be stored in a password protected shared network drive. There are currently no plans for future research. However new questions may come up from this study that may be addressed by reanalyzing the collected data. If patients specifically request to withdraw their data from the data stored for future use, they must do so in writing, which will be kept on file. Their data will be segregated from the rest of the data and not used for future analysis. However it will be stored for analysis of the present study and as per rules of publication, for at least 7 years post-publication.

IV. RISK/BENEFIT ASSESSMENT

- 1. Risk.** TBI subjects may fatigue easily. We will ensure that subjects are given adequate rest breaks to prevent them from becoming fatigued during the experimental protocol. Each testing session will not last longer than 3 hours on a single day. The assessments and videotapes may pose risks to confidentiality which will be minimized by following the protections below. The emotional function videos will assess physiological responses to neutral, happiness, sadness, fear and disgust-inducing video clips which mimic everyday experiences which may produce these emotions. The unwarmed startle probe may be emotionally distressing. If a previously undetected, potentially significant medical problem is observed, the subject will be informed of it by the-PI by phone so that the matter may be investigated further with the subject's regular physician.

Transcranial Direct Current Stimulation (tDCS), a non-invasive neuromodulatory technique that alters neuronal excitability using a low direct current delivered to the frontal cortex with saline-soaked sponge scalp electrodes. TDCS modulates the firing rates of individual neurons, and influences dopaminergic, adrenergic, and serotonergic neural circuits (Boggio, Rigonatti et al. 2008; Nitsche, Boggio et al. 2009). tDCS utilizes low intensity direct current, which is known to have anti-seizure effects. Reversing the pathological alterations back to normal with tDCS presents a potential therapeutic option for persons with cognitive and emotional dysfunction post-TBI. Past research has demonstrated that tDCS safely improves depression in a general psychiatric population (Boggio, Rigonatti et al. 2008) and holds promise as a highly innovative therapy that may result in a substantial quality of life improvement in patients with TBI. Six weeks after the completion of tDCS treatment, its effects were still sustained and significant. Transcranial direct current stimulation will be provided by a saline-soaked pair of surface sponge electrodes (35 cm²) delivered by a FDA-approved battery-driven, constant current stimulator (Fisher Wallace Cranial Stimulator, Fisher Wallace Laboratories, New York). Major safety parameters of electrical stimulation utilizing direct current (as opposed to devices producing alternating current) are Current Density {A/cm²} = stimulation strength {A}/electrode size {cm²} X total stimulation durations(s) (Nitsche, Liebetanz et al. 2003). Therefore these major parameters of safety are determined by the size of the electrodes, the intensity of the current and the duration of the stimulation. A comprehensive review by Sundaram and colleagues (2009) evaluated existing tDCS protocols involving human subjects from the perspective of aforementioned safety limits. Potentially damaging value of Current Density is 25 mA/cm², while existing tDCS protocols deliver Current Density ranging between 0.02-0.08 mA/cm², well within safety limits. Potentially damaging value of Total Carge is 216C/cm², while existing protocols deliver 0.002-0.068C/cm², which is a well-within safety limit. The parameters of stimulation in our study will be: size of electrodes 36 cm², intensity 2mA, stimulation time 20 min per sessions, which translates into Current Density 0.08 mA/cm² and Current Density 0.08 mA/cm² and Total Charge 0.068 C/cm², which is in concordance with parameters of other tDCS studies and well within the safety limits.

To stimulate the DLPFC, the anode electrode will be placed over F3 according to the 10-20 international system for EEG electrode placement (Fregni, Boggio et al. 2005). The cathode will be placed over the contralateral supraorbital area. We will focus our investigations on the left DLPFC, as modulation of this area by tDCS has been shown to

enhance working memory (Fregni, Boggio et al. 2005) which also demands similar attentional resources as emotional control (Anderson and Knight 2010). A constant current of 2 mA intensity will be applied for 20 min. These stimulation parameters have been used in other tDCS studies (Fregni, Boggio et al. 2006; Fregni, Boggio et al. 2006; Stevanovic 2011), and have been shown to produce effects outlasting the stimulation, well within safety limits [see detailed review in (Stevanovic 2011)]. To date, the above described stimulation parameters have not elicited any treatment-related serious adverse events. Non-serious adverse events infrequently occurring in tDCS studies (Poreisz, Boros et al. 2007) include short-term headache, transient fatigue or disturbed sensation under electrodes during the stimulation, such as mild tingling, itching or mild burning that is a natural sensation related to low-intensity current passing through the scalp. The sensation typically disappears immediately after the tDCS stimulation. Further, tDCS has not presented with any potentially harmful pharmacological interactions (Nitsche and Paulus 2001; Poreisz, Boros et al. 2007). Thus study participants receiving tDCS maintain their usual pharmacological regimen.

Patients having brain scans as part of the research study may feel claustrophobic from lying in the magnetic tube. There is risk of injury if there are metal objects in the body. Subjects will be required to fill out a questionnaire indicating if this is true. The subjects will be told that they may hear loud noises while in the MRI machine. The distress will be minimized by providing the subjects with ear plugs and limiting the duration of time in the MRI machine to less than 30 minutes. The research MRI scans will be read by the investigators within one week of the exam. If a previously undetected, clinically significant finding is observed the subject will be notified by the PI by phone so that the matter may be investigated further with the subject's regular physician.

Protection against Risks. Potential risks and discomfort will be minimized to the greatest extent possible through such procedures as appropriate training of personnel and monitoring of subjects. Subjects may take rest breaks as needed during therapy and assessment sessions so that the risk of fatigue is minimized.

In order to minimize any emotional distress, we will explain to the subjects that they may become upset so that they are forewarned. We will explain that the emotional stimuli are similar to everyday experiences that evoke emotional responses. The examination of emotional reactivity and the treatment included in the study will examine how well they cope with real-life situations that may be upsetting to them. In case of any adverse event or difficulty, including events unrelated to the study that make it difficult to continue with the protocol, the subject will be withdrawn from the study and referred for treatment, counseling, or other necessary follow-up. Physicians ([name] and [name] Im) and a neuropsychologist ([name]) who specializes in treating patients with TBI are included on the team, and will be available to counsel, treat and provide other necessary follow-up in such an event. This study does not provide financial assistance for medical or other injury-related costs.

Risks to confidentiality will be minimized by maintaining a secure, immobile computer database. Subjects will be identified by code rather than by name.

Potential Benefits to the Subjects. As this is a treatment study, tDCS and cognitive training intervention will be provided to participants. This intervention is intended to benefit participants by improving their attentional and emotional function. TDCS modulates the firing rates of individual neurons, and influences dopaminergic, adrenergic, and serotonergic neural circuits (Boggio, Rigonatti et al. 2008; Nitsche, Boggio et al. 2009). Reversing the pathological alterations back to normal with tDCS presents a potential therapeutic option for persons with cognitive and emotional dysfunction post-TBI. Past research has demonstrated that tDCS safely improves depression in a general psychiatric population (Boggio, Rigonatti et al. 2008) and holds promise as a highly innovative therapy that may result in a substantial quality of life improvement in patients with TBI. TDCS treatment offers several potential advantages, including: i) faster onset of action than antidepressants, ii) non-systemic treatment that can be used in patients who cannot tolerate antidepressants or psycho stimulants due to side-effects, medication interactions, and comorbidities; iii) no observed adverse interactions between pharmacological agents and tDCS; iv) usefulness for patients with low performance status, because it does not require patients' focused attention or physical effort; and v) it is well-tolerated, brief, safe, and easy to administer. In addition, because no adverse interactions have been observed between pharmacological agents and tDCS, it can be used as adjuvant therapy in patients who report partial relief from pharmacological treatment.

V. INVESTIGATORS' QUALIFICATIONS AND EXPERIENCE (CVs attached)

[name] is the original Principal Investigator and Director of the Motor Recovery Research Laboratory at the Rusk Institute of Rehabilitation Medicine. She and her delegates will be responsible for administering the assessments, the tDCS intervention, and data analysis.

[name] will be continuing the role of PI once [name] leaves.

[name] is an Attending Physician in the inpatient brain injury unit. He will refer patients with TBI eligible for the study to the PI.

[name] is the Director of Psychology Research at the Rusk Institute of Rehabilitation Medicine. She will be responsible for supervising neuropsychological testing and training.

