There will be a total of 4 testing visits (visits 1, 2 3 and 4 as described above) prior to starting the study, after which, subjects will receive treatment for visits 5-16). After completion of treatment, the subjects will then be re-tested on the baseline assessments and resting state MRI (Post-intervention Visits 17, 18, 19 and 20the total amount of visits for TBI subjects will be 20.). Healthy Control Subjects will have a total of three testing visits (1-3) only.

The subjects with TBI will then be randomly assigned to one of two groups, each consisting of 10 subjects. Subjects will be randomized by a simple randomization method. They will have a 50/50 chance of being in either group by flipping of a coin. Randomization will be carried out by the PI. Subjects and study personnel performing assessments and data analysis will be blind to group assignment. Only the PI will be unblinded.

The experimental group will receive active tDCS for 20 minutes and computerized cognitive training twice a week for 30-45 minutes for 6 weeks as described below. The control group will receive sham-tDCS 20 minutes and computerized cognitive training for 30-45 minutes twice a week for 6 weeks (12 training sessions). The sham group will not receive real tDCS after completion of the study.

In addition, we will conduct a qualitative interview with each of the subjects. Giorgi's phenomenology (Giorgi 1985; Kleiman 2004) is the method that will be used to describe the experiences of persons undergoing tDCS for treatment of TBI. In-person audio-taped interviews will be conducted at the completion visit by an experienced qualitative interviewer and immediately transcribed verbatim. Interviews are expected to range from 30 minutes to 1 hour. Each of the subjects will be asked the open-ended question, "Please tell me about your experience undergoing tDCS for the treatment of traumatic brain injury." Probes included the following questions: "What was the experience like for you? What should we continue to do and what should we change to make the experience better for patients?" Themes will be derived using the constant comparative method (Sandelowski 1995; Thorne 2000).

II. CHARACTERSTICS OF THE RESEARCH POPULATION

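### The statement that only the PI is unblinded cannot be reconciled with how the sham is delivered, or with the shared pool of staff named for stimulation, assessment and analysis

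*Protocol*

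**What the plan says.** **Who is blind.** Section I.3 (Study Design): "Subjects and study personnel performing assessments and data analysis will be blind to group assignment". It adds "Only the PI will be unblinded" and "Randomization will be carried out by the PI", the method being a coin flip.

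**Who delivers the stimulation, and how the sham is made.** Section III.1.5: "Transcranial direct current stimulation will be delivered by trained study personnel". In the active arm the current runs for 20 minutes. In the sham arm the electrodes are placed in the same way, but "the stimulator will be turned off after 5 seconds". The procedure is justified as one that has "been used to blind patients to the stimulation condition". There are 12 sessions.

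**Who assesses and analyses.** Section V says of the PI: "She and her delegates will be responsible for administering the assessments, the tDCS intervention, and data analysis". The MARS paragraph in Section III.1.1 has that scale completed by the PI or delegates. Section III.2, Data Monitoring item (2), says: "Independence of judgment will be assured by using independent assessors for outcomes". Section III.2 also blinds the coders of facial behavior to diagnostic status, meaning patient or control. It does not mention treatment arm.

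**The concern.** A sham protects the comparison only as far as the people who measure the outcome stay unaware of the arm. Here the sham is justified only as a way to keep patients unaware. Nothing is said about keeping the operator unaware, and the operators come from the same group that is named for testing and analysis. The PI, who is unblinded by design, belongs to that group too.

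At stake is the Aim 2 contrast of active against sham stimulation, wherever a score depends on an observer's judgement or on how an examiner administers a test. Section III.2 also intends to use this analysis to size later trials, so a biased difference would carry forward into them. Loss of assessor blinding cannot be repaired once the post-treatment data have been collected.

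**Working it through.** No calculation in the protocol is in question. The check is to set the passages side by side.

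**Step 1: does the operator know the arm?** The person running a session must either let the current run for 20 minutes or see that it stops after 5 seconds. An automatic cut-off, a coded sham mode or a masked display would break that link, but Section III.1.5 describes none of them. The sentence is passive and names no operator, so operator knowledge is an inference. It is the natural one.

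**Step 2: who is the operator?** There are two possibilities.

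| If the device is run by | Then |
|---|---|
| Trained staff other than the PI (Sections III.1.5 and V) | People besides the PI are unblinded, contrary to Section I.3 |
| The PI alone | Section I.3 can stand on this point, but Sections III.1.5 and V describe delivery wrongly or too loosely |

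Either way, at least one passage has to change.

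**Step 3: does the unblinding reach the outcomes?** Section V lists the PI and delegates for all three tasks, and Section III.1.1 draws the MARS rater from the same people. Two routes follow:

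- **Through a delegate.** A delegate who has run the device could be the assessor, unless roles are divided. No passage divides them.
- **Through the PI.** The PI randomizes and is declared unblinded, yet is listed for assessment, MARS rating and data analysis. This conflicts with the blind-assessor sentence in Section I.3 whoever operates the device.

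**Step 4: when does it bite?** Section III.1.5 places baseline testing before randomization, so baseline scores cannot be influenced by knowledge of arm. The exposed scores are those after treatment (Visits 17 to 20). Subtracting baseline does not help. The condition-by-session contrast is

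(post − pre, active) − (post − pre, sham).

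If knowledge of arm shifts post-treatment scores by *a* in the active arm and *s* in the sham arm, the contrast moves by *a* − *s* in full, because the pre scores are untouched.

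**Step 5: which measures are exposed?**

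- **More exposed:** the MARS, which rests on observed behavior, and the examiner-administered neuropsychological tests.
- **Less exposed:** ANT-R reaction times (computerized), the TAS (self-report) and the physiological recordings.
- **Unclear:** facial coding. Coders work from muted video and are blind to diagnosis, but the protocol does not say that they are blind to arm.

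**The case against.** The strongest reply is that the protocol already contains the rule. Section I.3 says that those who assess and analyse will be blind, and Section III.2 promises independent assessors. Anyone who learned a subject's arm at the device could not assess that subject without breaking Section I.3. This stands. A reader might infer that nothing forbids an operator from assessing, and that would be wrong. What is missing is the division of roles that would make the rule work, and Sections III.1.1 and V describe staffing that does not provide it.

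Other stronger readings are also unsupported:

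- **That the statement about the PI is simply false.** Section III.1.5 does not exclude the PI as operator, and Section V lists the PI for the stimulation. The supportable claim is that the passages are unreconciled.
- **That one person treats, tests and analyses the same subject.** Section V assigns collective responsibility and would also fit divided roles.
- **That the MARS is an Aim 2 endpoint.** Section III.2 runs the ANOVA on variables related to executive attention and emotional appraisal without listing them, and names the MARS only for correlation with the ANT-R. Section III.1 does repeat the outcome measures after treatment, so the MARS may be intended, but that is an inference.
- **That re-training time could drift between arms under an unblinded operator.** No passage says that the operator supervises the training or sets its length. The 30 to 45 minute range is the same in both arms.

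It can also be said that this is a pilot with a sample size the protocol itself calls arbitrary. That limits what the trial can conclude, but it does not remove bias from the difference that is carried into later planning.

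**Conclusion.** The concern holds as an unreconciled contradiction about blinding and role separation. Section I.3 confines unblinding to the PI. Sections III.1.5 and V put other staff at a device whose sham, as described, reveals the arm. Sections III.1.1 and V draw raters and analysts from those same staff and from the unblinded PI. The stated intention of blind, independent assessment is on record, but the described staffing does not secure it.

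The conclusion rests on one inference, that no masked sham mode exists because none is described. If the device has such a mode, the operator part falls away. The conflict over the PI as assessor, rater and analyst remains.

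No numerical size can be given. A false-positive rate would need an assumed rating shift and a pre/post correlation, and the protocol supplies neither. The exposure is confined mainly to rater- or examiner-dependent measures after treatment and should not be read as affecting the whole battery.

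**What to change.** 1. In Section I.3, state that the PI and the stimulation operators are unblinded.
2. In Section III.1.1 (MARS), Section III.2 (Data Monitoring item 2) and Section V, state that neither the PI nor anyone who has operated the stimulator for a subject may test, rate, code or analyse that subject's post-randomization data. Barring operators alone is not enough, because a PI who randomizes but never runs the device would still be an unblinded rater.
3. Divide the existing delegates into operators and blinded assessors or analysts, recorded in a delegation log. Alternatively, have the already unblinded PI operate the device. Make Section III.1.5 agree with whichever is chosen, and say there whether the sham is masked from the operator.
4. In Section III.2, state that facial coders are blind to treatment arm as well as to diagnostic status.

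The cost is protocol wording and a delegation log. Existing delegates are divided by role, so no new staff are needed. The downside is somewhat less flexibility in scheduling.
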